# TREATMENT PLAN

REGIMEN DESCRIPTION								
Agent	Premedications; Precautions	Dose	Route	Schedule	Cycle Length			

BMS-986253*	No specific premedications or precautions	2400mg	IV over 120 minutes (+/- 10 minutes) before Nivolumab	Days 1, 15 of each cycle	
Nivolumab	No specific premedications or precautions	480mg	IV over 30 minutes (-5 minutes/+10 minutes) after BMS-986253	Day 1 of each cycle	4 weeks (28 days)
Degarelix	No specific premedications or precautions	240mg loading dose (cycle 3), 80mg (cycle 4- 6)	SQ after BMS- 986253 and Nivolumab	Day 1 of each cycle	

\* For patients weighing less than 35 kg BMS-986253 should be infused over 180 minutes. .

# **MEASUREMENT OF EFFECT**

#### **Biochemical Response/Progression**

All participants who complete study requirements after treatment with androgen deprivation therapy using Degarelix with either Nivolumab alone or Nivolumab plus BMS- 986253 will follow-up until they reach PSA relapse defined as at least two serial rises in PSA ( $\geq 2$  weeks apart) with PSA >0.2ng/ml for radical prostatectomy patients or PSA >2.0ng/ml for patients who received other primary therapies (e.g. radiation cryotherapy, brachytherapy).

#### Radiographic Progression

Radiographic progression will be defined as the appearance of new lesions for men who initially have biochemically recurrent, non-metastatic disease. For men with metastatic disease at baseline, Response Evaluation Criteria in Solid Tumors version 1.1 (RECIST) will be used for soft tissue lesions and Prostate Cancer Clinical Trials Working Group 3 (PCWG3) criteria will be used for osseus disease

#### STATISTICAL CONSIDERATIONS

#### Study Design and Sample Size

This is a multicenter, 2-arm phase 1b/2 trial to evaluate the activity of Nivolumab or Nivolumab plus BMS-986253 with IADT using Degarelix in men with hormone sensitive prostate cancer with a rising PSA. The primary endpoints of this trial is rate of PSA recurrence 10 months after start of therapy. Within the context of this proposed trial, we will target a decrease in post-therapy PSA recurrence at 10 months of 25% compared to a historical recurrence rate of 50% with intermittent ADT alone. Probabilities of type I and type II error will be set at 0.05 and 0.2 respectively. The study will include a total of 23 evaluable patients per arm. This study design yields at least 80% power to detect a PSA recurrence rate of 25% at 10 months after start of therapy (compared to the null hypothesis of 50%) at a significance level of 5%. Accounting for a dropout rate of 20%, we will plan to enroll a total of 30 patients per arm.

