This is a two-arm, multicenter, phase 1b/2 study to assess the efficacy of immunotherapy with either Nivolumab (anti-PD-1) or Nivolumab plus BMS-986253 combined with ADT using Degarelix (LHRH antagonist) for men with hormone-sensitive prostate cancer and a rising PSA (30 patients per group), with a primary endpoint of rate of PSA recurrence 12 months after completion of therapy. We hypothesize that immunotherapy with either Nivolumab alone or Nivolumab plus BMS-986253 combined with Degarelix will decrease the percentage of men with hormonse-sensitive prostate cancer and a rising PSA who have PSA recurrence 12 months after completion of therapy from 50% (historical reference; McKay RR et al, 2016) to 25%. Baseline and on-treatment biopsies will be obtained for a subgroup of patients with biopsy accessible lesions in each group to characterize the immune effects of therapy.

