# **STUDY OBJECTIVES**

## Primary Objective

- Determine the rate of PSA recurrence defined as a PSA >0.2ng/ml for radical prostatectomy patients or PSA >2.0ng/ml for patients who received other primary therapies (e.g. radiation, cryotherapy, brachytherapy) at a time point of 10 months after start of therapy.
- Determine the safety and tolerability of either nivolumab or nivolumab plus BMS-986253 in combination with degarelix in men with hormone-sensitive prostate cancer.

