#### Secondary Objectives

- To assess the relapse-free survival (RFS) after recovery of testosterone with relapse defined as a PSA >0.2ng/ml for radical prostatectomy patients or PSA >2.0ng/ml for patients who received other primary therapies and recovery of testosterone defined as a testosterone (>150ng/dl).
- Determine the % change in PSA to immunotherapy by comparing the PSA prior to and following 8 weeks of immunotherapy and before initiation of ADT.

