# **STUDY DESIGN**

# General Design

This is a multi-center, two-arm, open-label, phase 1b/2 study evaluating the anti-tumor effect of either Nivolumab alone or Nivolumab plus BMS-986253 with androgen deprivation therapy using Degarelix in men with hormone-sensitive prostate cancer and a rising PSA. Patients will be recruited from outpatient clinics at participating sites and randomized to either Nivolumab alone (Arm A) or Nivolumab plus BMS-986253 (Arm B).

**Study Interventions:** Eligible patients in Arm A will receive Nivolumab every 4 weeks for 2 doses and then Nivolumab + Degarelix every 4 weeks x 4 doses. Eligible patients in Arm B will receive Nivolumab every 4 weeks x2 doses + BMS-986253 every 2 weeks x 4 doses and then

Nivolumab every 4 weeks x 4 doses + BMS-986253 every 2 weeks x 8 doses + Degarelix every 4 weeks x 4 doses.

Schedule of Evaluations: During treatment patients will have safety assessments including routine bloodwork and physical examinations at each visit. (See Section 12 for detailed study evaluations and the study schedule). Safety evaluations will also occur until 100 days after the last treatment doses.

The primary endpoint will be evaluated by assessing the PSA 10 months after start of therapy. PSA and serum testosterone will be checked monthly during treatment (+/- 3 days), the end of treatment visit (+/- 1 week), every 2 months (+/- 1 week) or until progression of disease during year 1 of follow up and every 3 months (+/- 1 month) or until progression of disease during year 2 of follow up. Sera, whole blood and CBC with differential will be collected for immunoassays at initiation of immunotherapy, at initiation of degarelix, end of treatment visit and 10, 14 and 18 month (+/- 1 week). Patients will also have CT or MRI scans (chest, abdomen and pelvis) and bone scan at screening, end of treatment and 10 months after start of therapy. Toxicity evaluation will utilize CTCAE v5.0 criteria.

**Duration of Treatment:** Subjects will receive treatment for a total of 6 months or intolerable toxicity or side effects.

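### The Introduction ties the 50% null and 25% target to 12 months after completion of therapy, but the primary test applies them at 10 months after start; if the Introduction is right, ADT alone could pass

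*Combined protocol and SAP*

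**What the plan says.** The Introduction describes the study "with a primary endpoint of rate of PSA recurrence 12 months after completion of therapy". Its hypothesis is a reduction in "PSA recurrence 12 months after completion of therapy from 50% (historical reference", with a citation) to 25%. This is the only place where the 50% carries a reference.

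The rest of the document uses another time. The Primary Objective measures recurrence "at a time point of 10 months after start of therapy". General Design agrees: "The primary endpoint will be evaluated by assessing the PSA 10 months after start of therapy". Number of Subjects and Study Design and Sample Size also use 10 months after start and keep 50% and 25%; the latter targets "a decrease in post-therapy PSA recurrence at 10 months of 25% compared to a historical recurrence rate of 50" percent and attributes that rate to intermittent ADT alone, without a citation.

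Study Endpoints then tests each arm against 50% with a one-sided binomial test. Both arms receive nivolumab and degarelix, and no arm receives ADT alone. The primary endpoint does not require testosterone to have recovered. The secondary relapse-free survival objective does, with a threshold of 150 ng/dl.

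**The concern.** With six months of treatment, 12 months after completion falls at about month 18 from start. Month 10 from start is only about 4 to 4.5 months after completion. The same null and target cannot be assumed to hold at both times, and nothing in the documents converts the rate from one to the other or justifies 50% at month 10.

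Counted cumulatively, recurrence by month 10 cannot exceed recurrence by month 18. So if the 50% belongs to 12 months after completion, it is too high as a month-10 null unless nobody first recurs between the two times. Some men may also still have PSA held down by ADT at month 10.

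The 50% is the whole comparator for the primary test. If it is too high, an arm could be declared active although the immunotherapy adds nothing. The secondary log-rank comparison between arms does not use the 50%, but it cannot isolate nivolumab because both arms receive it. It therefore offers no protection.

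**Working it through.** **Inputs.** Null 0.50, target 0.25, alpha 0.05, type II error 0.2, 23 evaluable and 30 enrolled per arm (Study Design and Sample Size); one-sided binomial test per arm (Study Endpoints); treatment for 6 months (General Design), given as six 28-day cycles with degarelix on day 1 of cycles 3 to 6 (Treatment Plan).

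**1. The plan's own figure reproduces.** With X the number of recurrences among 23:
- P(X ≤ 7 | 0.50) = 0.0466, and P(X ≤ 8 | 0.50) = 0.105, so the rule is 7 or fewer.
- Power = P(X ≤ 7 | 0.25) = 0.804.

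The sample-size arithmetic is sound. With 30 evaluable the rule is 10 or fewer, alpha 0.0494.

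**2. Timeline (30.44-day months).** Six cycles = 168 days = 5.5 months; month 10 = day 304. The gap from completion to month 10 is 10 − 6 = 4.0 months, or (304 − 168)/30.44 = 4.48 months if counted from day 168.

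**3. Without any curve.** The chance that an add-on with no effect passes, by true ADT-alone rate at month 10:

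| True rate | 23 evaluable (≤ 7) | 30 evaluable (≤ 10) |
|---|---|---|
| 50% | 0.047 | 0.049 |
| 45% | 0.12 | 0.14 |
| 40% | 0.24 | 0.29 |

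**4. With assumed curves that reach 50% at 12 months after completion.** The month-10 rate is 1 − 0.5^((t/T)^k), with t the time from clock start to month 10, T the time from clock start to the 50% point, and k the Weibull shape.

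| Assumed curve | Month-10 rate | Pass, n = 23 | Pass, n = 30 |
|---|---|---|---|
| Early rise from completion, k = 0.5, t/T = 4/12 to 4.48/12 | 33 to 35% | 0.50 to 0.43 | 0.60 to 0.53 |
| Constant hazard from start, 10/18 | 32% | 0.54 | 0.65 |
| Constant hazard from last degarelix injection, 5.40/12.92 | 25% | 0.80 | 0.89 |
| Constant hazard from completion, 4/12 to 4.48/12 | 21 to 23% | 0.92 to 0.87 | 0.97 to 0.94 |
| Late rise from completion, k = 2, 4/12 to 4.48/12 | 7 to 9% | > 0.99 | > 0.99 |

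For example, 1 − 0.5^(4/12) = 0.206 and P(X ≤ 7 | 23, 0.206) = 0.917.

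**5. Allowing for men already above threshold at completion.** The Primary Objective reads as PSA status at month 10, so men whose PSA never fell below threshold would count. Let f be their fraction, with constant hazard in the rest and 50% overall at 12 months. The month-10 rate is 1 − (1 − f)(0.5/(1 − f))^(t/12). For t = 4.0 to 4.48 and n = 23, the pass probability is 0.77 to 0.71 at f = 10%, 0.55 to 0.50 at 20%, 0.32 to 0.29 at 30%, and about 0.14 at 40%.

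**The case against.** The weight of the text favours month 10. The objective, the schedule and both sample-size statements agree on it, and imaging is planned at "bone scan at screening, end of treatment and 10 months after start of therapy". The Introduction may simply be stale, and then the remedy is a text correction. The sample-size text does pair 50% with month 10; what is missing is a justification. The time, clock start, ADT course and PSA definition behind the 50% lie in a cited study that the documents do not reproduce, so an invalid test is not proven.

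All of that stands, and it is why the consequence is stated conditionally. It does not remove the problem: agreement among sections on when to measure says nothing about whether 50% is the right rate then, and the only cited 50% is attached to the other time.

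It is also fair that the curves in step 4 assume no recurrence before the clock starts, so their lower end is not a bound. Step 5 relaxes this and the pass probability falls, but every case shown remains well above 0.05. The curve-free figures in step 3 are the safest to rely on.

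**Conclusion.** The plan is wrong as written. It states two primary endpoint times with one pair of rates, and the validity of the primary test depends on which is right. The conflict itself is certain.

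The inflation of type I error is conditional on 50% belonging to 12 months after completion. Its direction then needs only that some men first recur between months 10 and 18. Its size is an assumption: from 0.12 per arm if the ADT-alone rate at month 10 is 45% to about 0.9 under constant hazard from completion, against a nominal 0.05. The curve-based sizes also assume that the reference ADT course and population resemble this trial's. If the source supports 50% at a time matching month 10, the test stands and only the Introduction needs correcting.

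**What to change.** First check in the cited source the time, clock start and PSA definition behind the 50%, and state them in the sample-size section.

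- **If they match month 10 after start:** correct the Introduction and state the match. This costs a text change.
- **If the time is 12 months after completion**, choose one:
  - **(a) Move the primary assessment there.** Keep 50% against 25% and 23 evaluable, and correct Primary Objective, General Design, Number of Subjects, and Study Design and Sample Size. PSA and testosterone are already scheduled "every 2 months (+/- 1 week) or until progression of disease during year 1 of follow up", so no PSA visit is added. The readout comes about 8 months later (18 − 10) and no longer coincides with the month-10 imaging. The 20% dropout allowance must also hold for longer: 30 × 0.8 = 24, one above 23, and exact power at 24 is 0.766.
  - **(b) Keep month 10.** Replace 50% with the source's rate at the matching time, restate the target, critical value and power, and correct the Introduction, Number of Subjects, Study Design and Sample Size, and Study Endpoints. This is a redesign: either enrolment grows or lower power is stated and accepted.

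For (b), an illustration with the target set at half the null (exact one-sided 5%):

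| Null | Rule and power, n = 23 | Rule and power, n = 30 | First n with power ≥ 0.80 |
|---|---|---|---|
| 20.6% | ≤ 1, 0.30 | ≤ 2, 0.39 | 79 |
| 32% | ≤ 3, 0.49 | ≤ 5, 0.66 | 46 |
| 40% | ≤ 4, 0.50 | ≤ 7, 0.76 | 36 |

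These sizes depend on the halved target. Carrying both rates back by constant hazard instead (20.6% against 1 − 0.75^(4/12) = 9.1%) gives 61 per arm. They are also first crossings: with the halved target, power stays at or above 0.80 only from 91, 54 and 39.

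Reporting the proportion with testosterone above 150 ng/dl beside the primary rate would help interpretation at no extra data cost. It is desirable, but the conflict can be resolved without it.

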#### Study Endpoints

We will use one-sided binomial tests to compare the post-therapy PSA recurrence rate in each arm with the historical recurrence rate of 50%. To compare the secondary outcomes between the two arms, Kaplan-Meier estimators and log-rank tests will be used to compare time-to-event variables (e.g., time to PSA recurrence, time to recovery of testosterone, and time to next anti-cancer treatment); Chi-squared tests will be used to compare incidence rates (e.g., incidence of metastases); t-tests will be used to compare continuous measurements (e.g., changes immune cell density and proximity). We will set the nominal significance level at 5%. Only patients undergoing randomization to the treatment arms will be used for comparison between the treatment arms.

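### The randomised comparison of time to PSA recurrence is a valid but unadjusted log-rank test; pre-specifying adjustment for pre-dose PSA relative to each man's own threshold is a cheap, possibly useful gain

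*Combined protocol and SAP*

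**What the plan says.** Study Endpoints (Statistical Considerations) introduces the between-arm analyses with "To compare the secondary outcomes between the two arms" and then states that "Kaplan-Meier estimators and log-rank tests will be used to compare time-to-event variables". Time to PSA recurrence is one of its examples. The level is a nominal 5%, and sidedness is not stated for these comparisons. Neither this section nor any other names a covariate, a stratified test, a Cox model or a stratification factor for the randomisation.

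The Primary Objective has "PSA recurrence defined as a PSA >0.2ng/ml for radical prostatectomy patients or PSA >2.0ng/ml for patients who received other primary therapies". Biochemical Response/Progression uses the same two levels and adds a requirement for at least two serial rises. A PSA before treatment is needed for the secondary objective on percentage change in PSA, and primary therapy must be known to apply the right threshold.

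The only power statement concerns each arm against a historical 50%: "This study design yields at least 80% power to detect a PSA recurrence rate of 25% at 10 months after start of therapy". No power, event count or hazard ratio is given for the log-rank comparison.

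**The concern.** If two men have the same depth of suppression and the same regrowth rate, the one whose entry PSA is higher relative to his own threshold reaches that threshold sooner. A baseline value that is plausibly related to outcome is therefore available before the first dose, and the planned test ignores it. In time-to-event data, leaving out a strong prognostic covariate tends to pull the estimated arm effect toward the null and lower power, even under randomisation.

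At stake is the efficiency of the named randomised test of whether adding BMS-986253 delays PSA recurrence, in about 60 men. With 30 per arm and no stated stratification, chance imbalance in entry PSA or primary therapy is also plausible. An adjustment chosen after seeing the data would carry less weight than one fixed now.

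**Working it through.** **1. The plan's own figure.** Inputs from Study Design and Sample Size: null 50%, alternative 25%, 23 evaluable per arm, 5% level. Exact one-sided binomial, rejecting at 7 or fewer recurrences: P(X ≤ 7 | 23, 0.50) = 0.0466 and P(X ≤ 7 | 23, 0.25) = 0.804. With 20% dropout, 23/0.8 = 28.75, so 29 against the 30 planned. The primary claim reproduces, and nothing below changes it.

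**2. The unadjusted log-rank test.** Assumptions not in the documents: 10-month recurrence of 50% against 25% between arms, exponential times, 30 per arm, two-sided 5%.
- HR = ln 0.75 / ln 0.50 = 0.415, so |ln HR| = 0.879.
- Events by 10 months: 30 × 0.50 + 30 × 0.25 = 22.5. By 30 months (6 months of treatment plus 2 years): 30 × (1 − 0.50³) + 30 × (1 − 0.75³) = 43.6.
- Schoenfeld power = Φ(|ln HR| × √(d/4) − 1.96). At 22.5 events: Φ(2.09 − 1.96) = 55%. At 43.6 events: Φ(2.90 − 1.96) = 83%.

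**3. Adding a prognostic baseline covariate.** Simulation, 4,000 trials per cell, marginal 10-month rates held at 50% and 25%. The covariate has log hazard ratio g per SD. The Cox test is a likelihood-ratio test with no small-sample correction.

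| g | 10 months: log-rank → Cox | 30 months: log-rank → Cox |
|---|---|---|
| 0 | 52% → 52% | 83% → 83% |
| 0.3 | 54% → 55% | 79% → 82% |
| 0.5 | 52% → 57% | 77% → 84% |
| 0.7 | 54% → 62% | 73% → 86% |
| 1.0 | 55% → 71% | 70% → 91% |

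The gain depends entirely on g, which the documents do not give.

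**4. Which covariate.** Write recurrence time as t = t₀ + (K − x)/r. Here x = ln(entry PSA / own threshold), K is the log depth of suppression and r is the regrowth rate. Raw PSA can order men wrongly: with assumed medians of 1.5 ng/ml after prostatectomy and 6 ng/ml after other therapy, the ratios are 1.5/0.2 = 7.5 and 6/2.0 = 3. The man with the lower PSA is further above his threshold.

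A simulation of this model (60% prostatectomy, three levels of noise in K and r, 2,500 trials per cell) gave these ranges over noise level and follow-up of 10 or 30 months:

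| Analysis | Power gain over log-rank (points) | Type I error |
|---|---|---|
| Unadjusted log-rank | – | 4.9-6.1% |
| Log-rank stratified by primary therapy only | −0.6 to 2.2 | 5.1-5.9% |
| Cox, log entry PSA | 0.2 to 3.1 | 6.0-6.6% |
| Cox, log(entry PSA / threshold) | 4.6 to 23.4 | 6.5-8.9% |
| Cox, log entry PSA plus primary therapy | 5.5 to 23.1 | 6.9-9.5% |

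The Monte Carlo standard error at 5% is √(0.05 × 0.95/2,500) = 0.4 points, so the inflation in the last two rows is real. Part of their gain is bought with extra false positives.

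**5. The gain with error controlled.** Two further simulations with both thresholds, 30 per arm and assumed inputs:
- Permutation p-value on the covariate-adjusted score (900 replicates, visit-grid ties, about 50 events): type I error 4-5%, against about 8% for the ordinary Cox-Efron test and about 6% for the log-rank. Power 53% → 54% with noisy suppression and 67% → 77% with less noise, a gain of 1 to 10 points.
- Log-rank stratified at the median of scaled PSA (1,000 replicates): type I error 5.3-6.7%, against 4.0-5.8% for the plain log-rank and 6.3-8.8% for Cox-Efron. Power 62% → 65%, 74% → 79% and 81% → 88%, a gain of 3 to 7 points. The Monte Carlo standard error here is √(0.05 × 0.95/1,000) = 0.7 points, so slight inflation of the stratified test is not excluded.

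**The case against.** The strongest reply is that nothing here is an error. A log-rank test is valid in a randomised comparison, and its type I error already allows for chance imbalance. The comparison is secondary in a phase 1b/2 trial, and no stated figure is wrong. All of that stands.

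It is also fair to say that entry PSA is at most a predictor. Men receive immunotherapy and then degarelix, so depth of suppression, testosterone recovery and regrowth rate all come between entry PSA and recurrence. The definition with two serial rises is not what a simple threshold-crossing simulation represents. A simulation that assumes the covariate matters will show that it matters. This stands too, and is why only a range is given.

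A reader might infer that entry PSA by itself fixes a man's distance to recurrence. The two thresholds are tenfold apart, so it does not, and raw entry PSA added only about 0 to 3 points. A reader might also infer that this log-rank test is the only randomised comparison of PSA recurrence. The lists in Study Endpoints are examples and include chi-squared tests of incidence rates, so that is not established.

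What survives is narrow. The relevant baseline information is already in hand, and fixing its use in advance costs little.

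**Conclusion.** This is a cheap improvement, not a defect. The unadjusted log-rank test is valid but may be less efficient than an analysis using pre-dose PSA scaled by the man's own threshold. With type I error controlled, the gain under assumed inputs is about 0 to 10 points of power, and nil if the scaled value is not prognostic. This rests on 30 per arm, a two-sided 5% level, and assumed distributions of entry PSA, suppression and regrowth. The documents give none of those distributions, so no single power figure should be quoted.

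Three stronger readings are not supported. First, larger gains of up to about 23 points come from an ordinary Cox test that rejects too often at this size. Second, the primary analysis is not weakened: the one-sided binomial tests and the 30 per arm are untouched. Third, the point does not extend to time to testosterone recovery. General Design says "PSA and serum testosterone will be checked monthly during treatment (+/- 3 days", which does not establish a pre-dose testosterone value, and no gain was calculated for that outcome.

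**What to change.** In Study Endpoints, pre-specify one of these for the between-arm analysis of time to PSA recurrence:

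- a log-rank test stratified by pre-dose PSA divided by the man's own threshold, for example above or below the median of that ratio; or
- a Cox model with arm and log(pre-dose PSA / own threshold), Efron ties, and a permutation p-value for the arm effect.

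The permutation step is needed because the ordinary Cox test ran at about 6-9% type I error. Efron ties are needed because visits 2 to 3 months apart produce many ties; with Breslow ties the gain largely disappeared. Use only a PSA taken before the first dose, not the 8-week value, which treatment may already have changed. Do not substitute primary therapy alone as the stratum, since that added almost nothing. Keep to this one covariate because events are few. Report the unadjusted log-rank test and the Kaplan-Meier curves alongside, and state the sidedness.

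The cost is SAP wording and a little more analysis. With the Cox option there is also a hazard ratio that is conditional on the covariate, and a proportional-hazards check. No new data are needed.

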# Exploratory Objectives

- To assess the anti-tumor immune response
  - Quantification of CD8 T cell, CD4 T cell, Treg, CD8/Treg, CD4/Treg, PMN-MDSC and other immune cell populations in a subset of patients (at least 10 per arm) with tumor specimens before and after treatment by immunohistochemistry (IHC). Immune cell density and proximity will also be assessed using polychromatic immunofluorescence.
  - Quantification a range of immunologic markers in a subset of patients (at least 10 per arm) with tumor specimens before and after treatment.
  - Quantification of tumor cell apoptosis by TUNEL and caspase-3 staining.
  - Quantification of circulating IL-8 and other cytokines before and after treatment and correlation with response to therapy.
  - Quantification of circulating PMN-MDSCs and other immune cell populations before and after treatment and correlation with response to therapy.

- Assess whether treatment can induce an increased IgG response to tumor antigens (epitope spreading) by comparing pre- and post-treatment sera.
- Assess the DNA or RNA-related molecular characteristics of tumor specimens and correlate with response to treatment (if adequate tissue available).

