#### Number of Subjects

The study will include a total of approximately 30 patients per arm to achieve at least 23 evaluable patients per arm. This study design yields at least 80% power to detect a PSA recurrence rate of 25% at 10 months after start of therapy (compared to the null hypothesis of 50%) at a significance level of 5%. Accounting for a dropout rate of 20%, we will plan to enroll a total of 30 patients per arm.

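### The t-tests on change in tissue immune measures fix the baseline slope at 1; ANCOVA on the same pairs risks little and may gain power at 10 patients per arm

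*Combined protocol and SAP*

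**What the plan says.** Patients are "randomized to either Nivolumab alone (Arm A) or Nivolumab plus BMS-986253 (Arm B"). The Introduction says that "Baseline and on-treatment biopsies will be obtained for a subgroup of patients with biopsy accessible lesions in each group". The Exploratory Objectives place immune cell counts "in a subset of patients (at least 10 per arm) with tumor specimens before and after treatment by immunohistochemistry (IHC"), and add density and proximity by immunofluorescence.

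The analysis rule is one clause of the Study Endpoints section: "t-tests will be used to compare continuous measurements (e.g., changes immune cell density and proximity"). The nominal level is 5%; whether the t-tests are one- or two-sided is not stated. That section introduces the rule as one for secondary outcomes, while the objectives list the tissue measures as exploratory. The supplied text names no ANCOVA, regression model or baseline covariate. The pre-treatment tissue value therefore enters the comparison only through subtraction.

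**The concern.** The tissue subset is where the plan can compare directly, in tumor, what adding BMS-986253 does to the immune infiltrate, and it may hold as few as 10 pairs per arm. A change score is the follow-up value minus exactly 1 times the baseline value. If the true regression slope of follow-up on baseline is well away from 1, the change score carries noise that an estimated slope would remove, and a real difference between arms is easier to miss. The baseline biopsy has already been taken, so removing that noise needs no new data. What is at stake is the power of an exploratory comparison. The validity of the test and the primary endpoint are not in question.

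**Working it through.** **The plan's own figures.** The only sample-size figure is for the primary endpoint. An exact one-sided binomial test with 23 evaluable patients, declaring success at 7 or fewer recurrences, has type I error 0.0466 under 50% and power 0.804 under 25%. This reproduces the stated 80% at 5%. Nothing below touches it. For the tissue comparison the documents state no power, effect size, SD or correlation, so there is no figure to reproduce.

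**Inputs.** From the documents: 10 patients per arm (the stated minimum, so N = 20), a 5% level, two randomized arms, paired tissue. Assumed: a two-sided test; baseline SD 1; follow-up SD k = 0.8, 1, 1.5 or 2; baseline to follow-up correlation ρ = 0.3, 0.5, 0.7 or 0.9; normal values; the same slope in both arms.

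**Variances per patient.**
- Change score: 1 + k² − 2ρk.
- ANCOVA: k²(1 − ρ²) × (N − 3)/(N − 4). The last factor is the price of estimating the slope; at N = 20 it is 17/16 = 1.0625.

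Before that factor, the change-score variance minus the ANCOVA variance is 1 − 2ρk + ρ²k² = (1 − ρk)², which is never negative. The ratio of ANCOVA to change-score variance is therefore at most 17/16, and reaches it only where ρk = 1.

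Example with k = 1, ρ = 0.5: change score 1 + 1 − 1 = 1.00; ANCOVA 0.75 × 1.0625 = 0.797; ratio 0.797. Example with k = 2, ρ = 0.5 (ρk = 1): change score 1 + 4 − 2 = 3.00; ANCOVA 4 × 0.75 × 1.0625 = 3.19; ratio 1.0625.

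**Variance ratio, ANCOVA to change score, N = 20.**

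| k | ρ = 0.3 | 0.5 | 0.7 | 0.9 |
|---|---|---|---|---|
| 0.8 | 0.533 | 0.607 | 0.667 | 0.646 |
| 1 | 0.691 | 0.797 | 0.903 | 1.009 |
| 1.5 | 0.926 | 1.025 | 1.060 | 0.826 |
| 2 | 1.018 | 1.062 | 0.985 | 0.577 |

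**Power.** In each cell the true difference was set so that the change-score t-test (18 degrees of freedom) has 60% power. ANCOVA (17 degrees of freedom) was then simulated with 100,000 trials per cell.

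| k | ρ = 0.3 | 0.5 | 0.7 | 0.9 |
|---|---|---|---|---|
| 0.8 | 86% | 81% | 77% | 78% |
| 1 | 76% | 70% | 64% | 60% |
| 1.5 | 63% | 59% | 58% | 68% |
| 2 | 59% | 57% | 61% | 83% |

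Where ρk = 1, ANCOVA has about 57% against 60%, a loss of about 3 points. If the t-test instead has 80% power, the loss is again about 3 points (about 77% against 80%). With no true difference, both methods reject in about 5% of trials.

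**Cross-check at a fixed effect.** With equal SDs and a true difference of 1.0 SD, the change-score test and ANCOVA have 43% and 58% power at ρ = 0.3, 56% and 66% at 0.5, 78% and 82% at 0.7, and 99.8% and 99.7% at 0.9. The pattern is the same: a clear gain at low to moderate correlation and none at 0.9.

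**The case against.** The strongest case against is that nothing here is wrong. The t-test on change is valid, the measures are exploratory, the plan claims no power for them, and the rule is a one-line summary with an example. All of that stands, and it limits the point to an optional improvement.

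It can also be said that a gain cannot be shown from these documents. That stands too. If treatment raises the spread of immune cell density, follow-up SD could exceed baseline SD. The Introduction's remark that ADT initially brings T cells into tumor makes this plausible. At k = 1.5 to 2 and ρ = 0.3 to 0.7, four of the six cells are small losses and the other two gain only 1 to 3 points. What remains is the asymmetry: the loss is bounded at about 3 points, while the gain reaches 16 points with equal SDs and 26 in the most favorable cell (86% − 60%).

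Ten per arm is a floor. A larger subset would shrink the cost of estimating the slope; at 15 per arm the bound is 27/26 = 1.04.

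Three stronger readings are tempting and not supported:
- A reader might infer that the plan ignores baseline. It does not: a change score uses baseline with a slope of 1.
- A reader might infer bias or a false-positive problem. Under randomization there is none from this choice.
- A reader might extend the point to the 8-week percentage change in PSA. Study Endpoints does not name PSA in the t-test rule, and the secondary objective describes a before-and-after comparison with no between-arm test. Any question about the scale for PSA is a separate one.

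**Conclusion.** The point holds as a matter of efficiency only and is minor. At the minimum subset size, estimating the baseline slope moves power from 60% to somewhere between about 57% and 86% over the assumed range. The gain is largest where correlation times SD ratio is far from 1; where that product is near 1, the gain is nil or slightly negative. The limit of about 3 points on the loss assumes a normal covariate and a common slope in the two arms. SDs, correlations, the two-sided test and the 60% anchor are assumptions, because the documents supply none of them.

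**What to change.** In Study Endpoints, replace the t-test clause for measures that have a baseline with wording such as: *Continuous measurements with a baseline value will be compared between arms by ANCOVA of the follow-up value on arm and baseline value, on a scale (raw or log) fixed for each measure before outcome data are seen.* Keep the t-test on change as a sensitivity analysis.

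No new patients, biopsies or assays are needed. The cost is one degree of freedom per model and, under the stated assumptions, at most about 3 points of power. It also requires a scale decision for each measure, including how zeros are handled if logs are used. That is real work, because the Exploratory Objectives list several cell populations, two ratios and an open-ended range of markers, and the documents offer no variance data to guide the choice.
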